1. Presence of DVT on pre-operative screening ultrasound study.
2. Massive tumor (>20 cm in greatest dimension)
3. Amputation of the affected leg as treatment for tumor.
4. Estimated blood loss >2 liters during surgery.
5. Surgical drain output >500 cc of bloody fluid during first 8 hours.
6. I.N.R. >1.3 pre-operatively or > 1.5 post-operatively.
7. Platelet count < 100,000 either pre-operatively or post-operatively.
8. Indwelling post-operative epidural catheter for pain control.
9. Age <30 years.
10. History of underlying bleeding disorder, such as hemophilia.
11. History of adverse reaction to heparin such as heparin-induced thrombocytopenia.
12. Severe liver or renal insufficiency.
13. History of hypertensive or diabetic retinopathy.
14. History of gastro-intestinal bleeding within 12 months.
15. Treatment with warfarin, clopidogrel, aspirin, NSAIDs, LMWH or other anti-coagulants for conditions.
16. History of stroke.
17. Women of childbearing potential having a positive serum or urine pregnancy test (hCG) at the time of pre-operative evaluation (within 7 days of surgery).
18. Women who are breast feeding.
19. Hemoglobin < 8.0 gm/dl
20. Platelet count < 100,000 /L
21. Alanine aminotransferase >100 IU/L
22. Aspartate aminotransferase > 100 IU/L

23. Direct bilirubin >0.5 gm/dL (the laboratory does not perform direct bilirubin if total bilirubin is below 0.2 mg/dl since direct bilirubin cannot be greater than total bilirubin).
24. Serum creatinine > 2.0 gm/dL
25. Patients taking COX-2 inhibitors.
26. Patients who have fragmented mechanical heart valves.

Study Design

The study design will be an open-label, non-randomized clinical trial involving 25 – 35 consecutive patients in each of the two groups. Historical controls from this institution will be used to compare peri-operative bleeding events, drainage, transfusion requirements, and re-operation rates in similar patients who did not receive chemical prophylaxis for DVT. Published historical controls will be used to compare the DVT rate. The rate of DVT will be measured in this study, but the primary objective is to examine bleeding complications at the surgical site. The sample size therefore is not calculated to establish efficacy, which has been demonstrated for patients in general in numerous previous articles.

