The study design will be an open-label, non-randomized clinical trial involving 25 – 35 consecutive patients in each of the two groups. To analyze wound complications historical controls will be identified through the Surgical Database maintained by the Section of Orthopaedics from this institution and will be used to compare peri-operative bleeding events, drainage, transfusion requirements, and re-operation rates in similar patients who did not receive chemical prophylaxis for DVT. Data from surgery, including drain output, transfusion requirements, wound complications, and re-operation for wound problems will be collected. To analyze DVT rates and to compare against patients who did not receive, data from the previously published article by Lin et. al. will be used for the control group of patients with mechanical compression stockings alone. Patients will receive a combination of dalteparin, bilateral TED hose, and bilateral mechanical compression stockings while in the hospital.

Method of DVT Prophylaxis

Patients will receive a combination of dalteparin, bilateral TED hose, and bilateral mechanical compression stockings while in the hospital.

The reason for employing both mechanical prophylaxis and dalteparin together is as follows. DVT prophylaxis is very difficult to achieve. The DVT rate is never zero. There is a very little, if any, adverse effects of using mechanical compression stockings. However, from the previous study at Memorial Sloan-Kettering, it is known that there is still a significant rate of DVT (17%) with mechanical prophylaxis. Dalteparin and other low molecular weight heparins may improve upon this rate. There is no contraindication to using both dalteparin and mechanical prophylaxis together. The study is not intended to show that dalteparin obviates the need for mechanical prophylaxis.

Patients should not receive other anti-coagulants, such as aspirin, non-steroidal anti-inflammatory drugs, and warfarin while on the study. Heparin should not be administered except for routine intravenous catheter flushes.

During surgery, patients will have TED hose and a mechanical compression stocking on the unaffected extremity. For the operative leg TED hose and mechanical compression stocking will be applied in the recovery room.

Patients will be mobilized out of bed with physical therapy as soon as deemed safe by the attending physician (generally post-operative day 1).

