The main purpose of this safety study is to evaluate the safety of dalteparin in patients undergoing orthopaedic oncologic procedures. There is remarkably little information for the drug in patient population. The main concern is that the drug could lead to increased bleeding, hematomas, seromas, and wound problems. The safety study is intended to gather preliminary data that potentially could be used to formulate a larger study on DVT prophylaxis. For the safety study, it seems reasonable to institute a stop rule. The stop rule will terminate the study in case the drug leads to an unacceptable rate of adverse events. The stop rules should not be based upon an arbitrary amount of post-operative drainage or weeks is a much better measure to use. This is discrete event that is a common final outcome for unacceptable wound bleeding, large seromas and hematomas, and other wound problems.

Two groups of patients will be evaluated in 2 independent cohorts, 1) patients who require major resection of sarcomas in the lower extremity, and 2) patients with metastatic disease of the lower extremity. There is little information about safety and efficacy of dalteparin in these two patient groups. Knowledge gained from the treatment of these patients will be used to design larger, more definitive studies. Twenty-five patients will be treated in the metastatic cohort and 30 patients in the sarcoma cohort. A total of 50 – 70 patients will be accrued on this study.

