Safety Monitoring. The primary endpoint for safety monitoring is the re-operation rate due to complications experienced by patients within the first 4 weeks after surgery. In the sarcoma group, surgery can be extensive and clinical experience indicates that approximately 10% of patients will require re-operation within 4 weeks.¹⁵⁻¹⁷ A 25% re-operation rate in this group of patients would be considered excessive. For the metastatic patient group, the surgery is typically less involved and the re-operation rate during the first 4 weeks is near zero.¹⁸ (we assume 3%) and a 15% re-operation rate would be considered excessive. We will monitor this endpoint separately for these two patient groups using the sequential probability ratio test (Goldman 1987).¹⁹ We assume a type 1 error rate of 5% for both treatment groups. Table 1 contains the stopping rules for each patient group. For example, in the metastatic group, if 2 patients in the first 8 treated require re-operations to amend primary surgical complications, the protocol will stop accrual in this group. Similar, if 4 of the first 8 patients in the sarcoma group require re-

operation, accrual in this patient group will stop. The probabilities of detecting excessive re-operation rates if the true rates are as high or higher than stated above using these two stopping rules are 6% and 72% for the metastatic and sarcoma patient groups, respectively.

Table 1. Stop trial for excessive re-operation rate if the number of re-operations at or larger than listed (No. Re-operations) are necessary in the number of patients treated.				
	Metastatic Patients			
No. Re-operations	2	3	4	
No. Patients	8	25	25	
	Sarcoma Patients			
No. Re-operations	4	5	6	7
No. Patients	8	16	26	30

Analysis Plan. Several additional safety and efficacy endpoints will be estimated. These include pre-operative DVT incidence, surgical drain output, the number of transfusions, post-operative DVT's and others. For continuous variables (e.g., surgical drainage, number of transfusions) data will be summarized using the mean (s.d.) and median (range). For categorical variables (e.g., DVTs, gender) data will be summarized in frequency tables. 95% confidence intervals will be estimated for all outcomes. For categorical outcomes, outcome estimates will be estimated with standard errors no larger than 9% and 10% for the sarcoma and metastatic patients, respectively.

Cost of Study

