The major cost of this study is the Doppler ultrasound test to detect lower extremity DVT's. The cost is \$475 per unilateral study and \$950 per bilateral study at MD Anderson Cancer Center. The medication will be provided by Pfizer. The institutional tax is 25%, but this is waived for direct patient charges (i.e., ultrasound studies).

Seventy patients are used as the basis for the cost analysis. It is anticipated that there will be 50 patients on protocol in the study. The cost estimate includes an additional 20 patients for attrition from the study or exclusion from study as a result of a positive screening Doppler ultrasound test. It is noted however that these patients do provide useful data and information that is part of the study. If there is zero attrition and no pre-operative DVTs, up to 10 additional patients will be included in each study group.

Research Related Items	Amount	Overhead (25%)	Notes
Protocol Approval Fee	\$1,000	n/c	Required institutional fee for review and approval of clinical trials.
PDMS User Fee	\$10,500	\$2,625	Required institutional fee for registration in PDMS - \$150/patient minimum.
Experimental Pharmacy Fee	\$7,000	\$1,750	Required institutional fee for experimental pharmacy handling/inventory control; \$100/patient
Diagnostic Imaging	\$96,250	n/c	Projected cost based on current rate. One bilateral Doppler ultrasound scan (\$950) + one unilateral scan (\$475) per patient = \$1375 per patient
Administrative and miscellaneous costs	\$7,000	\$1,750	\$100/patient for unforeseen laboratory tests, document preparation, and non-institutional overhead costs.
Sub-total	\$121,750	\$6,125	
Total	\$127,875		Direct cost per patient \$1,739 Indirect cost per patient \$87.50 Total cost per patient \$1,827

Revised 9/7/04

References

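### The plan lets each cohort reach 35 patients, but Table 1 stops at 25 metastatic and 30 sarcoma patients, so later patients have no stopping boundary

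*Combined protocol and SAP*

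**What the plan says.** The number of patients per cohort is given in several places, and the statements differ.

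- **Study Design**, which makes the statement twice, describes a trial "involving 25 – 35 consecutive patients in each of the two groups". No condition is attached.
- **Statistical Considerations** says "Twenty-five patients will be treated in the metastatic cohort and 30 patients in the sarcoma cohort". The next sentence gives total accrual as 50–70.
- **Cost of Study** says "It is anticipated that there will be 50 patients on protocol in the study". It budgets for 70: "The cost estimate includes an additional 20 patients for attrition from the study", or for exclusion after a positive screening ultrasound. It then adds: "If there is zero attrition and no pre-operative DVTs, up to 10 additional patients will be included in each study group".
- **Table 1** (Safety Monitoring) has its last metastatic entry at 25 patients and its last sarcoma entry at 30.
- **Analysis Plan** promises "standard errors no larger than 9% and 10% for the sarcoma and metastatic patients".

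On the purpose of the monitoring, Statistical Considerations says: "The stop rule will terminate the study in case the drug leads to an unacceptable rate of adverse events". No section gives a boundary beyond 25 and 30, or a method for extending Table 1.

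**The concern.** A sequential stopping rule is defined only up to its last listed patient. If a cohort may run to 35 and the table ends at 25 or 30, then 10 of 35 metastatic patients and 5 of 35 sarcoma patients are treated in a period when no number of re-operations triggers a stop. Re-operation within 4 weeks is the endpoint the plan chose for safety monitoring, so this gap is in the main protection the design offers.

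Two further problems follow. Staff who meet the gap may improvise a boundary, which changes the 5% error rate the plan assumes. And a sarcoma cohort closed at 25, the lower end of the Study Design range, would not deliver the stated 72% detection.

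**Working it through.** **Inputs, all from Safety Monitoring and Table 1.** Acceptable and excessive re-operation rates: 3% and 15% (metastatic), 10% and 25% (sarcoma). Type 1 error: 5% per group. Boundaries: metastatic 2 in 8, 3 in 25, 4 in 25 (the last is never active, because 3 in 25 stops sooner); sarcoma 4 in 8, 5 in 16, 6 in 26, 7 in 30.

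**Method.** Exact binomial recursion, checked after every patient. Let f(n,k) be the probability of reaching patient n unstopped with k re-operations:

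f(n,k) = f(n−1,k)(1−p) + f(n−1,k−1)p, for k below b(n),

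where b(n) is the smallest listed count whose patient number has not yet been passed. Probability at or above b(n) is added to the stopping probability. Checking only at the listed patient numbers gives the same results.

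**Step 1: reproduce the plan's figures.**

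| Cohort | Last patient | Stops at acceptable rate | Stops at excessive rate |
|---|---|---|---|
| Sarcoma | 30 | 5.01% | 71.7% |
| Metastatic | 25 | 5.05% | 76.1% |

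The sarcoma row matches the stated 5% and 72%, and the metastatic 5% also matches. The maximum standard error is √(0.25/n): 10.0% at n = 25, 9.1% at n = 30 and 8.5% at n = 35. The stated 10% and 9% are therefore the values for 25 and 30. The statistical section is built on those sizes.

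**Step 2: run to 35 with Table 1 as printed.** The overall stopping probabilities are the same as in Step 1, because nothing can stop after the last entry. At the excessive rates:

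- Pass the last boundary: 1 − 0.7613 = 0.2387 (metastatic); 1 − 0.7175 = 0.2825, or 28.3% before rounding (sarcoma).
- At least one re-operation among the later patients: 1 − 0.85^10 = 0.803; 1 − 0.75^5 = 0.763.
- Both: 0.2387 × 0.803 = 19.2%; 0.2825 × 0.763 = 21.5%.
- Pass, then at least two: 10.9% and 10.4%.
- Pass, then finish above the excessive rate: 0.8% reach 6 or more of 35 metastatic (6/35 = 17.1%); 1.0% reach 9 or more of 35 sarcoma (9/35 = 25.7%).

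**Step 3: what improvised extensions do to the false-stop rate.**

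| Extension to 35 | Metastatic, at 3% | Sarcoma, at 10% |
|---|---|---|
| Last count carried forward (3; 7) | 9.6% | 7.1% |
| Next count appended (4; 8) | 5.6% | 5.3% |

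**Step 4: close sarcoma at 25.** Detection at a 25% rate is 63.8%.

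**Step 5: totals.** 25 + 30 = 55 treated, against 50 on protocol in Cost of Study. With 55 treated, 70 − 55 = 15 remain for attrition and exclusion, against the 20 stated.

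**The case against.** The best defence is that the figures count different things: 25 and 30 are patients treated, while 25–35 and 50–70 are patients accrued, with the difference lost to attrition or a positive screening scan. Cost of Study defeats this, because its extra 10 per group are added precisely when nobody is lost. Those patients would be treated.

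A second point has more force. Expansion under Cost of Study needs both zero attrition and no pre-operative DVT. If 50 were screened, the chance of no DVT would be 36% at 2% prevalence, 7.7% at 5% and 0.5% at 10% (0.98^50, 0.95^50, 0.90^50; the prevalences are assumptions). Several exclusions can only be judged during or after surgery, so some attrition is likely. By that route few cohorts would reach 35. Study Design, however, allows 25–35 without condition, so the contradiction remains.

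Three smaller points stand as qualifications:

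- Reaching 35 per group from Cost of Study assumes its 50 splits 25/25, which it does not say. That split does fit 25–35 per group and 50–70 in total. Added to 25 and 30 instead, the extra 10 would give 35 and 40, or 75 in all, above the 70 maximum.
- The metastatic row of Table 1 is irregular: it lists both 3 and 4 re-operations at 25 patients, and the stated 6% detection does not reproduce. That is a separate matter, but the metastatic figures here depend on the row as printed. If the 3 belonged at 16 patients (an assumption), 37.9% rather than 23.9% would pass the last boundary, and 30.5% rather than 19.2% would pass and then have a later re-operation.
- The budget totals do not affect monitoring, and 5.3% for sarcoma is only slightly above 5%.

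**Conclusion.** The concern holds. The plan gives conflicting cohort sizes for a quantity its safety stopping rule depends on. If enrolment runs to 35, 10 metastatic and 5 sarcoma patients have no boundary, and at the excessive rates about one cohort in five passes the last boundary and then has a re-operation that no count can act on. If sarcoma closes at 25, detection is 63.8% rather than 72%.

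The practical harm is limited. The gap opens only when a cohort passes its last boundary and accrual continues, and about 1% of cohorts at the excessive rates would pass and then finish above those rates. These results assume Table 1 as printed, independent patients with a constant re-operation rate, and outcomes known in time to act on them. The plan should be corrected, but the design does not fail because of it.

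**What to change.** State one maximum number treated per cohort in Study Design, Statistical Considerations and Cost of Study, and make Table 1 cover that number.

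**Simplest route: keep 25 and 30.**

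- Replace the 25–35 range in both Study Design statements with 25 metastatic and 30 sarcoma patients treated, 55 in all.
- Start the accrual range at 55 or more.
- Change the 50 on protocol to 55, and describe the remaining 15, up to 70, as the allowance for attrition and screening exclusion.
- Delete the clause that adds up to 10 patients per group.

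This costs wording only: no extra patients, and the 70-patient budget is unchanged.

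**If 35 per group is wanted:** have the statistician recompute Table 1 to 35 at the plan's own rates (3%/15% and 10%/25%) and 5% error. Adding only the next count at 35 gives 5.6% and 5.3%, so the whole boundary needs recalculation if 5% is to be met. This costs one recalculation.

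Under either route, restate the type 1 error and detection probabilities for the chosen maximum; if 35 is kept, update the standard errors as well.

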The hypothesis is that the drug is safe for the patient population identified in this study. Most of the published safety data on the drug pertains to general orthopaedic patients and not to orthopaedic oncology patients. This study is intended to provide preliminary data on benefits and risks for orthopaedic oncology patients.

Orthopaedic oncology encompasses a wide array of patients. Some patients are healthy and normal except for their tumor. Other patients may be moribund with multiple co-morbidities. Some patients require a relatively small procedure to remove the tumor, while others require massive resections and reconstructions. The risk of post-operative bleeding complications for these patients would be expected to vary considerably.

As the first step toward establishing the use of dalteparin in orthopaedic oncology patients, it is proposed that two target populations be studied. One group of patients is

comprised of those with metastatic disease in the lower extremity. The other group of patients is composed of those who require major resection of sarcomas of the lower extremity.

The two groups of patients are inherently different. The patients with metastatic disease of the lower extremity are an important group since they encompass a large population of patients. These patients are believed to be at the highest risk for DVT. They tend to be older, more sedentary, less mobile, and have multiple comorbid conditions. These patients may be ideal candidates for treatments with dalteparin. The patients typically undergo a limited excision or curettage followed by an intramedullary rod, plating, cementation, hip arthroplasty or knee arthroplasty. The patients typically do not have much post-operative bleeding or drainage, since the skeletal defect is filled with bone cement. There is typically no significant dead space after surgery in which a large hematoma or seroma could form.

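### The only formal stopping rule counts re-operations, so a death from bleeding or a wound complication without re-operation enters it as a non-event

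*Combined protocol and SAP*

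**What the plan says.** The Statistical Considerations section of the combined protocol and SAP gives the rule a broad purpose: "The stop rule will terminate the study in case the drug leads to an unacceptable rate of adverse events". Its Safety Monitoring paragraph then names a single event as the primary endpoint for monitoring, the "re-operation rate due to complications experienced by patients within the first 4 weeks" after surgery. Table 1 stops a group on the "number of re-operations at or larger than listed (No. Re-operations) are necessary in the number of patients treated". The metastatic example reads: "if 2 patients in the first 8 treated require re-operations to amend primary surgical complications, the protocol will stop accrual in this group". The numerator is therefore re-operations and the denominator is everyone treated.

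For sarcoma, the acceptable rate is that "approximately 10% of patients will require re-operation within 4 weeks", and "A 25% re-operation rate in this group of patients would be considered excessive". The metastatic rates are 3% and 15%. Type 1 error is set at 5% per group. The stated probabilities of detecting excessive re-operation are 6% (metastatic) and 72% (sarcoma).

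The plan gives a reason for its choice. It rejects an arbitrary drainage amount and treats re-operation as a discrete event to which wound bleeding, seromas, hematomas and other wound problems commonly lead.

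Endpoints of Analysis lists seven outcomes, among them transfusion and hemoglobin change, symptomatic pulmonary embolus, and bleeding at distant sites. The Analysis Plan paragraph estimates and summarises additional endpoints with 95% confidence intervals and attaches no stopping threshold to them. Death is not among the seven endpoints and is not part of the rule. Nothing says how a patient who dies before 4 weeks is counted.

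**The concern.** The purpose is wider than the event. A fatal bleed or wound complication in a patient who never returns to theatre is the harm that the trial most needs to notice. Under Table 1 that patient uses up a place in the denominator and leaves the event count unchanged. Death also ends any chance of a later re-operation. The direction is therefore unfavourable: this kind of death lowers the monitored re-operation fraction.

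At stake is the behaviour of the only formal safety guard in a study whose primary purpose is bleeding safety. Such a death would still be seen by the investigators, but no pre-specified rule would respond to it.

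**Working it through.** **Inputs.** Boundaries (Table 1): metastatic 2/8 and 3/25; sarcoma 4/8, 5/16, 6/26 and 7/30. Cohorts: 25 and 30. Acceptable and excessive rates: 3% and 15%; 10% and 25%. Table 1 as read shows both 3 and 4 re-operations at 25 metastatic patients. I use 3, because any group that reaches 4 by patient 25 has already reached 3.

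**Method.** Exact binomial enumeration: a group stops when cumulative events reach r at or before patient n. Looking after every patient, or only at the tabulated n, gives the same stopping probability.

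**Step 1: reproduce the plan.** For the metastatic group with event rate p,

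P(stop) = P(≥2 of 8) + P(0 of 8) × P(≥3 of 17) + P(1 of 8) × P(≥2 of 17).

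- p = 3%: 0.0223 + 0.7837 × 0.0134 + 0.1939 × 0.0909 = 0.0505 before rounding of the terms.
- p = 15%: 0.3428 + 0.2725 × 0.4802 + 0.3847 × 0.7475 = 0.761.

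The same enumeration over the four sarcoma boundaries gives 0.050 at 10% and 0.718 at 25%.

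The 5% error in both groups and the 72% for sarcoma reproduce. The printed 6% for the metastatic group does not; 76% is my recomputed figure. That is a separate matter and this point does not depend on it.

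**Step 2: the rule as written.** Suppose re-operation stays at its acceptable rate and a further share q of patients die of bleeding or a wound complication without re-operation. The event rate in the rule stays at 3% or 10%, so P(stop) stays at 5.05% or 5.0% for every q. This needs no assumption about q.

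**Step 3: count those deaths, Table 1 unchanged.** The event rate becomes 3% + q or 10% + q. The documents give no value of q, so the range is assumed.

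| q (points) | Metastatic rate | P(stop) | Sarcoma rate | P(stop) |
|---|---|---|---|---|
| 0 | 3.0% | 5.05% | 10.0% | 5.0% |
| 0.2 | 3.2% | 5.8% | 10.2% | 5.4% |
| 0.5 | 3.5% | 7.1% | 10.5% | 6.1% |
| 1.0 | 4.0% | 9.4% | 11.0% | 7.3% |
| 3.0 | 6.0% | 21% | 13.0% | 14% |

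If q is unavoidable background, these are type 1 errors. If q is caused by the drug, they are chances of a warranted stop that the present rule forgoes.

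**Step 4: death before a possible re-operation.** If an assumed 5% of patients die before they could be re-operated, the excessive rates become 15% × 0.95 = 14.25% and 25% × 0.95 = 23.75%. P(stop) falls from 76% to 73% and from 72% to 66%.

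**The case against.** The strongest reply is that re-operation was chosen for a reason. It is discrete, hard to dispute, and matches the surgical-site objective. Bleeding that does not lead back to theatre is partly covered, since transfusion, hemoglobin change and distant bleeding are collected and reported. All of this stands. It justifies keeping re-operation as the core event, but it does not say what happens to a patient who dies first.

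Four stronger readings are tempting, and the documents do not support them.

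- A reader might infer that the stated detection probability is wrong unless all harm leads to re-operation. The plan claims only to detect excessive re-operation rates, and that claim holds whatever other harm occurs. Treating 15% or 25% as total serious harm would be the reader's redefinition.
- A reader might take "Other patients may be moribund with multiple co-morbidities" (Introduction) as evidence that early deaths will be common here. The sentence describes orthopaedic oncology in general, before the two groups are selected. The exclusion criteria remove heavy operative bleeding, coagulopathy, recent gastro-intestinal bleeding and severe liver or renal insufficiency.
- A reader might conclude that all major bleeding can be added with Table 1 unchanged. Three extra points already give 21% and 14% type 1 error. If uncounted events were one fifth or one third of the composite at the acceptable rates, the metastatic rate would be 3%/0.8 = 3.75% or 3%/(2/3) = 4.5%, with error 8.2% or 12.0%. The sarcoma rate would be 10%/0.8 = 12.5% or 10%/(2/3) = 15%, with error 11.8% or 21.8%. The 3% to 5% bleeding in the drug background is not limited to major bleeding, so it is only an upper illustration.
- A reader might think that the change needs no new data. The monitoring described is in hospital, and deaths would have to be recorded and attributed to 4 weeks.

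**Conclusion.** The concern holds in a narrow form. The sole formal guard scores a bleeding- or wound-related death without re-operation as a non-event, and the plan leaves the handling of death unstated. That outcome follows from counting re-operations among patients treated; the documents do not say it in words.

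The size in this trial cannot be known, because no rate of such deaths is given. What is certain is that the rule's chance of stopping does not rise with them. Removal of patients by early death is a modest effect (Step 4, on an assumed 5%). The cost of counting these deaths is also modest if they add no more than about 1 point at the acceptable rate, which is an assumption that the sponsor should confirm. The gap lies in the stopping rule only: other bleeding outcomes are still collected and reported.

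**What to change.** 1. Define the stopping-rule event as re-operation for a complication, or death attributed to bleeding or a wound complication, within 4 weeks of surgery, at most one event per patient.
2. Report deaths from other causes before 4 weeks beside the rule, so that those patients are not shown as event-free.
3. Keep Table 1 if attributed deaths are expected to be rare at the acceptable rate. State the rate assumed and the resulting type 1 error from Step 3.
4. If non-fatal major bleeding without re-operation is also to count, define it, and recalculate the acceptable rate, the excessive rate and Table 1 before use.

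The cost of items 1 to 3 is a definition sentence, a restated error rate, 4-week recording and attribution of deaths, and a somewhat higher chance of a false stop. Item 4 is optional and costs a redesign of the boundaries.

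### The 6% detection probability given for the metastatic stopping rule does not follow from Table 1: the printed rule gives 76%, and Table 1 lists two thresholds at 25 patients

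*Combined protocol and SAP*

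**What the plan says.** The relevant text is in Statistical Considerations, under Safety Monitoring, and in Table 1.

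- **Endpoint and method.** Re-operation for complications within 4 weeks of surgery is the primary endpoint for safety monitoring. On method the plan says: "We will monitor this endpoint separately for these two patient groups using the sequential probability ratio test".
- **Metastatic design rates.** The assumed rate is 3%, and "a 15% re-operation rate would be considered excessive".
- **Sarcoma design rates.** About 10% is expected and 25% is excessive.
- **Error rate.** "We assume a type 1 error rate of 5% for both treatment groups".
- **Stop criterion.** The caption of Table 1 begins: "Stop trial for excessive re-operation rate if the number of re-operations at or larger than listed". A count equal to the listed number therefore stops accrual.
- **Metastatic boundaries.** Table 1 lists 2, 3 and 4 re-operations at 8, 25 and 25 patients. The prose confirms the first: "if 2 patients in the first 8 treated require re-operations to amend primary surgical complications, the protocol will stop accrual in this group".
- **Sarcoma boundaries.** 4, 5, 6 and 7 re-operations at 8, 16, 26 and 30 patients.
- **Cohort sizes.** "Twenty-five patients will be treated in the metastatic cohort and 30 patients in the sarcoma cohort".
- **Stated detection.** The probabilities for the "two stopping rules are 6% and 72% for the metastatic and sarcoma patient groups, respectively".

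**The concern.** A monitoring rule that stops 5% of the time at an acceptable rate and only 6% of the time at five times that rate (15% against 3%) barely tells the two apart. Taken at face value, the metastatic cohort would have almost no protection from the study's main safety rule, while the sarcoma rule beside it has 72%. Either the rule is badly built or the figure is wrong. A review board judging the monitoring plan needs to know which.

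Table 1 raises a second question. In the sarcoma rows each further re-operation comes with a larger number of patients, and the last entry is the cohort size. In the metastatic rows, 3 and 4 share the same 25 patients. Read literally, the 4-in-25 column can never act, because 3 in 25 has already stopped accrual. One of the entries may be a misprint, and the two columns imply different final thresholds.

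**Working it through.** **Inputs.** Metastatic: N = 25, acceptable rate 3%, excessive rate 15%, stop at 2 in 8, 3 in 25 or 4 in 25. Sarcoma: N = 30, rates 10% and 25%, stop at 4 in 8, 5 in 16, 6 in 26 or 7 in 30. All come from Statistical Considerations and Table 1. No outside figure is used.

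**Method.** Exact binomial recursion, patient by patient, removing any path that reaches a boundary. Cumulative counts never fall and the threshold is constant between listed patient numbers, so looking after every patient or only at the listed numbers gives the same answer.

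**1. Reproduce the plan's own figures first (sarcoma).** P(stop | 25%) = 71.7% (stated 72%) and P(stop | 10%) = 5.01% (stated 5%). The method therefore matches the plan's.

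**2. Metastatic rule as printed (2 in 8, then 3 in 25).** Let X be the count in the first 8 patients and Y the count in the next 17.

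P(stop) = P(X ≥ 2) + P(X = 0)·P(Y ≥ 3) + P(X = 1)·P(Y ≥ 2)

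- At 15%: 0.3428 + 0.2725 × 0.4802 + 0.3847 × 0.7475 = 0.3428 + 0.1309 + 0.2876 = **0.7613**
- At 3%: 0.0223 + 0.7837 × 0.0134 + 0.1939 × 0.0909 = 0.0223 + 0.0105 + 0.0176 = **0.0505** (the terms are rounded)

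The stated 5% type 1 error is reproduced. The stated 6% detection is not.

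**3. Lower bound.** The first term, P(X ≥ 2 | 15%) = 1 − 0.2725 − 0.3847 = 0.3428, is the 2-in-8 boundary alone. Later boundaries can only add to it, so any rule that keeps 2 in 8 detects at least 34.3%.

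**4. Other readings of the two 25-patient columns (N = 25).** If only 4 in 25 follows 2 in 8, the thresholds for Y rise by one. At 15%: 0.3428 + 0.2725 × 0.2444 + 0.3847 × 0.4802 = 0.5942.

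| Reading | Stop at 15% | Stop at 3% |
|---|---|---|
| 2 in 8, 3 in 25 (4 in 25 redundant) | 76.1% | 5.05% |
| 2 in 8, 3 in 24, 4 in 25 | 73.8% | 4.7% |
| 2 in 8, 3 in 20, 4 in 25 | 66.5% | 3.6% |
| 2 in 8, 3 in 16, 4 in 25 | 62.1% | 3.0% |
| 2 in 8, 4 in 25 only (same as 3 in 9) | 59.4% | 2.6% |

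Requiring counts strictly above those listed, against the caption, still gives 53.4%.

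**5. Where 6% would come from.** The printed rule stops with probability 0.06 at a true rate of about 3.2%, close to the acceptable rate and far from 15%.

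**6. What the repeated 25 is worth.** At 15%, 4 in 25 instead of 3 in 25 costs 76.1 − 59.4 = 16.7 percentage points. At a true rate of 20%, detection is 90.8% with 3 in 25 and 80.4% with 4 in 25.

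**7. Simulation check.** One million simulated cohorts at 15% gave 0.343 (2 in 8 alone), 0.762 (3 in 25), 0.595 (4 in 25 only) and 0.738 (3 in 24, 4 in 25).

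**The case against.** Four points can be made for the plan.

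*The range assumes 25 patients.* Study Design allows 25 to 35 patients per group, and Cost of Study allows up to 10 more in each. If the second 25 is the misprint, 4 belongs to a larger number and accrual continues to it, detection rises above 76%: 78.7% for 4 in 30 and 84.2% for 4 in 35, with false stops of 5.2% and 5.6%. This is correct, but Statistical Considerations sets the metastatic cohort at 25. With 25 patients, moving the 4 to a larger number leaves 76.1% and 5.05% unchanged. The larger figures are also further from 6%.

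*The digit may have been lost when the PDF was read.* This cannot be ruled out. A sentence earlier in the same section is visibly incomplete, and Table 1 was machine-read too. The arithmetic is certain for the text as supplied; whether the source contains the slip is not. Hence the source check comes first.

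*The 6% is descriptive.* It sets no boundary and no sample size, and it understates protection. That stands, and it limits the point to a correction the plan should make.

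*The literal text settles the repeated 25.* Under the caption's criterion 3 in 25 governs, and that reading best matches the stated 5%. This is a fair inference, but a safety table should not need one. With exactly three re-operations, the third after patient 8, one column stops accrual and the other implies continuing.

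**Conclusion.** The concern holds. The stated 6% is not a property of the metastatic rule in Table 1. The rule as printed detects a 15% re-operation rate with probability 76.1%, 70 points above the stated figure, at a 5.05% false-stop rate. Readings of the two 25-patient columns span 59.4% to 76.1%, given a cohort of 25, the 2-in-8 boundary and the caption's criterion. Of the four stated operating characteristics, this is the only one that fails to reproduce.

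A dropped digit (76% printed as 6%) is the likeliest explanation, but it is an inference. The error misreports the protection and does not itself weaken it. The repeated 25 is a separate ambiguity that does bear on a boundary, and the documents do not settle which entry is intended. The plan should correct both; neither invalidates the design.

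**What to change.** 1. Check the 6% and both 25-patient columns against the source document.
2. Reconcile the metastatic rows of Table 1 so that each threshold has one clear patient number and no column is redundant.
3. Restate detection at 15% and type 1 error at 3% for the confirmed boundary:
   - 76% and 5.05% if 3 in 25 stands as printed;
   - 59% and 2.6% if only 4 in 25 applies after 2 in 8;
   - the value for the confirmed number (59% to 74%, and 2.6% to 4.7%) if 3 belongs to between 9 and 24 patients and 4 in 25 is kept.
4. State the cohort size behind the figures. If the metastatic cohort may run past 25, recompute for that size.

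The cost is one probability to restate and one table entry to reconcile. Sample size does not change. The final threshold changes only if the confirmed boundary differs from 3 in 25. If the source already reads 76%, the first part closes and only the repeated 25 remains.
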